7. DATA CONVENTION AND RELATED DEFINITIONS

7.1 Baseline Definition

For all parameters, baseline will be defined as the last available value before the first treatment.

7.2 Duplicate Data

For unplanned duplicate data within protocol-specified visit duration, the last measured value will be used for the analysis. If it is not possible to identify the “last measured value” the average of the duplicate values will be used.

No data will be excluded. All collected data will be listed.

7.3 Handling of Missing Data

All data will be used as observed, and no imputations will be made for any missing data point. All summaries will be based on observed data only.

7.4 Multicenter Clinical Trials

This is a multi-center clinical trial.

7.5 Multiple Comparisons and Multiplicity

Not applicable for this study.

7.6 Covariates and Prognostic Factors

Not applicable for this study.

7.7 Stratification Factors

Not applicable for this study.

7.8 Standard Calculations

7.8.1 Age

Age will be calculated as the number of completed years between the date of informed consent and the subject's birth date.

$$\text{Age (years)} = \text{integer of}[(\text{date of informed consent} - \text{date of birth}) / 365.25 + 0.5]$$

7.8.2 Body Mass Index (BMI)

BMI will be calculated using height (in cm) and weight (in kg) according to the formula noted below.

$$\text{BMI (kg/m}^2\text{)} = \text{weight (kg)} / [(\text{height (cm)} / 100)^2]$$

7.8.3 Change from Baseline

Change will be calculated using according to the formula noted below.

$$\text{Change} = \text{Post Baseline Data} - \text{Baseline Data}$$

7.8.4 QTcF

QTcF will be calculated using according to the formula noted below.

$$QTcF = QT/RR^{1/3}$$
$$(RR=60/VR)$$

8. STATISTICAL METHODS

All data from this clinical trial will be provided in data listings, study drug, clinical trial center, subject, and time point (if applicable).

Data summary will be according to the variable type:

- Continuous data summaries will include:
 - Number of observations, mean, standard deviation, median, and minimum and maximum values.
- Categorical data summaries will include:
 - Frequency counts and percentages.

8.1 Summarizing and Tabulating the Collected Data

8.1.1 Subject Disposition and Withdrawals

There will be a detailed accounting of all subjects who sign an informed consent to participate in this study. The following will be summarized:

- The number of subjects who are enrolled
- The number of subjects who completed the Dose Titration
- The number of subjects who discontinued prior to completion of the dose titration
 - Reasons for discontinuation will also be summarized descriptively
- The number of subjects who completed the long term extension (Optional)
- The number of subjects who discontinued during the long term extension
 - Reasons for discontinuation will also be summarized descriptively

In addition, there will also be a listing of all discontinued subjects, which will provide the specific reason for discontinuation.

8.1.2 Demographics and Other Baseline Characteristics

Individual subject demographic and baseline characteristics including baseline disease status based on MMSE data (i.e., Mild: 21-30, Moderate: 10-20 and Severe: <10) will be summarized and also presented in subject data listings. Medical history data will be listed for safety population subjects.

8.1.3 Prior and Concomitant Medications

Prior and concomitant medications will be summarized for the Safety population.

All prior and concomitant medications recorded in the case report form will be using the most recent version of WHO Drug dictionary. Descriptive summaries will be prepared using the coded term. All prior and concomitant medications recorded in the case report form will be listed.

Medications entered as donepezil and memantine are captured in the Alzheimer's disease history and will not be included in the summary and listings of prior and concomitant medications.

8.1.4 Study Drug Administration

All available study drug administration data will be listed and/or summarized.

8.2 Analysis Primary Outcome Measure

The primary outcome measure for the study is the optimal initial dose and subsequent dose titration schedule of donepezil when given with solifenacin (15 mg/day or 20 mg/day).

Time to reach FID (First Intolerable Dose) for each patient will be presented as a subject specific listing. The proportion of subjects at the different MTD levels and those who were able to tolerate the highest dose of donepezil (i.e., 40 mg/day) and the MTD will be summarized descriptively. In addition, descriptive summary (i.e., n, mean, SD) of the highest dose reached will be presented.

The dose limiting side effect will be listed.

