2. PROTOCOL DESIGN

2.1 Design Overview

This is a Phase II, ascending dose study of CPC-201 in patients with dementia of Alzheimer's type to determine the optimal dose titration schedule. The study involves a step wise cohort design in two different patient populations: Group 1 will consist of patients who have been treated with donepezil 5 or 10 mg/day (given once daily) for at least 4 weeks just prior to Day1. Group 2 will consist of patients who have never been treated with donepezil before (donepezil naïve) or who have not received any other

AChEI for the past 6 months.

Original Plan

Donepezil dose will be increased at weekly intervals, in accordance with the schedules given below, to its first intolerable dose (FID) or maximum allowed dose (MAD) 60 mg/day together with solifenacin 15 mg/day. If a patient does not tolerate a donepezil dose higher than 40mg/day with solifenacin 15 mg/day, the solifenacin dose can be increased to 20mg/day per the Investigator's decision.

Cohort 1	1 st week: 20mg donepezil + 15mg solifenacin 2 nd week: 30mg donepezil + 15mg solifenacin 3 rd week: 40mg donepezil + 15mg solifenacin 4 th week: 50mg donepezil + 15mg (or 20mg) solifenacin 5 th week: 60mg donepezil + 15mg (or 20mg) solifenacin
Cohort 2*	1 st week: 20mg donepezil + 15mg solifenacin 2 nd week: 40mg donepezil + 15mg solifenacin 3 rd week: 60mg donepezil + 15mg (or 20mg) solifenacin
Cohort 3*	1 st week: 20mg donepezil + 15mg solifenacin 2 nd week: 60mg donepezil + 15mg (or 20mg) solifenacin

*: The dose titration schedule of Cohort 2 and 3 may be altered based on Cohort 1 result.

Patients reaching their FID or having completed one week treatment with MAD, have two options.

Option 1: Patient will be allowed to immediately enter a long term extension at their maximum tolerated dose (MTD) or MAD.

Option 2: Patients may choose not to enter the long term extension, in which case the Investigator will decide whether the patient should discontinue high dose of donepezil without down-titration, or whether donepezil should be dwn-titrated to their own standard of donepezil dose. Whatever the decision, the patient will be treated at least an additional 7 days with solifenacin 15 mg/day.

First Amendment

After 8 subjects in Cohort 1 and 1 subject in Cohort 2 were enrolled, the protocol was amended to add Cohort 1b and to limit to enroll only Group 1.

Patients currently treated with donepezil (Group 1) will receive solifenacin 15 mg/day

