2.3 Protocol Objective(s)

2.3.1 Primary Objective

To determine the optimal initial dose and subsequent dose titration schedule (rate and increment) for CPC-201.

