2.4 Study Outcome Measures

2.4.1 Primary Outcome Measure

The primary outcome for this study is optimal initial dose and subsequent dose titration schedule (rate and increment) for CPC-201.

- The FID of each patient
- The MTD of each patient

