6.2 MTD (Maximum Tolerable Dose) Evaluable population

The MTD evaluable population is defined as all subjects who completed the donepezil dose titration. This population will be used for summary of the primary study outcome.

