8.3 Analysis of Secondary Outcome Measures

8.3.1 Analysis of Safety and Tolerability Data

The Safety population will be used for all analyses of safety and tolerability. All Safety and tolerability parameters will be analyzed as a function of dose and dose titration schedule and be presented descriptively and as data listings.

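### SAP 8.2 calls 40 mg/day the highest dose without naming a cohort, though three of the four cohorts titrate to 60 mg/day, and it states no split by titration schedule

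*SAP*

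**What the plan says.** The primary objective in SAP 2.3.1 is "To determine the optimal initial dose and subsequent dose titration schedule (rate and increment) for CPC-201". SAP 2.4.1 names two subject-level primary measures: the maximum tolerated dose (MTD) and "The FID of each patient", FID being the first intolerable dose.

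SAP 8.2 then plans the following:

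- For FID: "Time to reach FID (First Intolerable Dose) for each patient will be presented as a subject specific listing".
- For MTD: the proportion of subjects at each level, together with "those who were able to tolerate the highest dose of donepezil (i.e., 40 mg/day) and the MTD will be summarized descriptively".
- As a further item, on the dose attained: "descriptive summary (i.e., n, mean, SD) of the highest dose reached will be presented".
- A listing of dose-limiting side effects.

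None of these items names a cohort or a schedule. The population comes from SAP 6.2: "The MTD evaluable population is defined as all subjects who completed the donepezil dose titration". It is not restricted to Cohort 3c.

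On maximum doses, SAP 2.1 titrates the original cohorts to "first intolerable dose (FID) or maximum allowed dose (MAD) 60 mg/day together with solifenacin 15 mg/day", repeats 60 mg/day for Cohort 1b, and stops Cohort 3c at 40 mg/day. Protocol 3.1 agrees: 60 mg/day, with 40 mg/day as the exception for Cohort 3c.

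On the split, Protocol 9.1.1 plans descriptive statistics for MTD and FID within each titration schedule. SAP 8.3.1 says "All Safety and tolerability parameters will be analyzed as a function of dose and dose titration schedule", but it does so under secondary outcomes and for the Safety population.

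**The concern.** The label and the design disagree. A category described as tolerating the highest dose is fixed at a level that is the top step in one of the four enrolled cohorts and an intermediate step in the other three. Taken at its word, SAP 8.2 counts a Cohort 1 subject who tolerates 40 mg and has an FID at 50 mg as having tolerated the highest dose.

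The missing split matters because the trial exists to compare titration schedules and has no hypothesis test. The descriptive tables in 8.2 are the whole primary result. If they cannot be read by schedule, they do not answer the objective. If the mean of highest dose reached is pooled, it combines 40 mg and 60 mg ceilings and shifts with the cohort mix even when tolerability is identical. Section 8.2 also leaves open whether a dose that was reached is one that was given or one that was tolerated.

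**Working it through.** **Step 1. Does 40 mg/day reproduce as the highest dose?** Schedules and enrolment are from SAP 2.1.

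| Cohort | Scheduled donepezil steps (mg/day) | Maximum | Enrolled |
|---|---|---|---|
| 1 | 20, 30, 40, 50, 60 | 60 | 8 |
| 2 | 20, 40, 60 | 60 | 1 |
| 1b | 10, 20, 30, 40, 50, 60 | 60 | 6 |
| 3c | 10, 15, 20, 25, 30, 35, 40 | 40 | not stated |

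The figure reproduces for Cohort 3c only. At least 8 + 1 + 6 = 15 enrolled subjects had a 60 mg maximum. 40 mg is, however, a step in all four schedules.

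**Step 2. How many subjects does the label not fit?** Cohort 3c enrolment *n* is assumed at 4, 6 or 12, from the planned 4 to 6 evaluable per group in up to two groups. The share is 15/(15 + *n*): 15/19 = 79%, 15/21 = 71%, 15/27 = 56%.

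**Step 3. Effect on the proportion.** Each 60 mg cohort subject with an MTD of 40 or 50 mg who is counted at the highest dose adds 1/8 = 12.5 points in Cohort 1, 1/6 = 16.7 points in Cohort 1b, or 1/15 = 6.7 points over the three cohorts, if all enrolled are evaluable.

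**Step 4. The wording supports several readings.** Take 15 invented MTDs in the 60 mg cohorts: 4 at 20, 2 at 30, 5 at 40, 2 at 50 and 2 at 60.

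- MTD exactly 40: 5/15 = 33%.
- MTD at least 40: 9/15 = 60%.
- MTD at the cohort's own maximum: 2/15 = 13%.

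**Step 5. Pooled mean of highest dose.** Suppose every subject reaches the maximum of his or her own cohort, with *m* subjects at 60 and *n* at 40. The mean is (60*m* + 40*n*)/(*m* + *n*). The SD is 20 × √[*mn*/((*m* + *n*)(*m* + *n* − 1))], all of it between cohorts. The value *m* = 8 is an assumed lower number of evaluable subjects.

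| Assumed *n* in 3c | Mean, *m* = 15 | SD, *m* = 15 | Mean, *m* = 8 |
|---|---|---|---|
| 4 | 55.8 | 8.4 | 53.3 |
| 6 | 54.3 | 9.3 | 51.4 |
| 12 | 51.1 | 10.1 | 48.0 |

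**Step 6. A constructed case, not a forecast.** Every subject tolerates 40 mg and nobody tolerates the next step (50 mg in Cohorts 1 and 1b, 60 mg in Cohort 2, none in 3c). MTD is taken as the last step before the FID. Section 8.2 read literally reports 100% tolerating the highest dose, while 0 of 15 tolerated their own 60 mg maximum. The pooled highest dose is 40.0 mg if it means tolerated. If it means given, it is (8×50 + 1×60 + 6×50 + 40*n*)/(15 + *n*) = 48.4, 47.6 or 45.9 mg for *n* = 4, 6 or 12.

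The optional 20 mg solifenacin dose is not modelled.

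**The case against.** The label conflict itself is hard to dispute; the case against concerns its reach.

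First, the split may already be promised. Protocol 7.3 treats FID as the tolerability assessment, Protocol 9.1.1 places MTD and FID under safety and tolerability, and SAP 8.3.1 analyses all such parameters by schedule. Nothing in 8.2 says cohorts will be pooled. A reader could infer the split, but 8.3.1 covers secondary outcomes in a different population. Where the SAP wants a cohort breakdown it says so, as for adverse events (8.3.1.1) and laboratory data (8.3.1.2). The gap in 8.2 remains.

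Second, the results in Steps 3, 4 and 6 need subjects stopped by an FID to count as having completed titration. Protocol 3.2 withdraws them from titration, and SAP 8.1.1 counts completers separately from those who discontinue earlier. This dependence is real. The inclusive reading is the more coherent one, since several MTD levels in 8.2 make little sense without these subjects. On the narrow reading everyone sits at the maximum of his or her own cohort, so the pooled mean reflects cohort mix alone, as in Step 5.

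Third, the harm is limited. The MTD-level proportions and the listings would still show a 60 mg cohort subject who stopped at 40 or 50 mg, and the study is descriptive. That stands: the fault lies in the label, the missing split and the pooled mean, not in the data.

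Fourth, 40 mg may have been meant as a level common to all cohorts. It would serve well as one, but the text calls it the highest dose and gives no such reason. Likewise, a dose reached most naturally means a dose given, since MTD already covers tolerance; one clause would settle it.

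**Conclusion.** The concern holds and should be fixed before reporting. The 40 mg/day label in SAP 8.2 contradicts the 60 mg/day maximum that both documents give for Cohorts 1, 2 and 1b, and the primary summaries lack the by-schedule presentation that Protocol 9.1.1 plans. FID, a primary measure, gets only a listing of time to reach it.

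The firm figures are that the label fits one cohort of four and that at least 15 enrolled subjects were in the others. The rest shows what could happen. Cohort 3c enrolment and the number evaluable are not in the documents, so the shares and pooled means are ranges over assumed values, and they are not estimates of an expected error.

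**What to change.** In SAP 8.2:

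- Reconcile the 40 mg/day label with the cohort-specific maxima in SAP 2.1 and Protocol 3.1. No view is taken here on which dose is right.
- For each of Cohorts 1, 2, 1b and 3c, report n/N tolerating that cohort's own maximum and, separately, n/N tolerating at least 40 mg/day as the common level.
- Present the MTD distribution, the FID and the highest dose reached by cohort, identifying subjects who reached the maximum without an FID.
- State whether the highest dose reached means given or tolerated, and whether subjects stopped by an FID belong to the SAP 6.2 population.

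As a clerical point, the Protocol Summary sentence on the options after one week at 40 mg/day omits the Cohort 3c qualifier that its counterpart in Protocol 3.1 carries. The two should be reconciled.

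The cost is SAP wording and a few small tables from data already collected. The downside is more small tables and no single pooled mean.

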8.3 Analysis of Secondary Outcome Measures

8.3.1 Analysis of Safety and Tolerability Data

The Safety population will be used for all analyses of safety and tolerability. All Safety and tolerability parameters will be analyzed as a function of dose and dose titration schedule and be presented descriptively and as data listings.

8.3.1.1 Adverse Events

Adverse events will be classified by system organ class (SOC) and preferred term (PT) according to the most recent version of MedDRA dictionary.

TEAE are defined as events with an onset on or after administration of the first dose of study drug. TEAEs will be summarized, System Organ Class, and preferred term. The following TEAE summaries will be provided:

- Top line summary table including
 - all treatment emergent Adverse Events (TEAEs), treatment related TEAE and treatment unrelated TEAE,
 - Serious treatment emergent Adverse Events (STEAEs), treatment related STEAE and treatment unrelated STEAE
 - Deaths
- Overall (*i.e.*, regardless of severity or relationship to treatment)
- By cohort (*i.e.*, 1, 2, 1b, 3c)
- By study phase (*i.e.*, titration and long term extension)
- By severity grade (mild, moderate, severe)
- By relationship to study drug (definitely, probably, possibly, not related)

Unless otherwise specified, at each level of subject summarization, a subject will be counted only once. If there is more than one occurrence of an event, the event of the worst severity or the worst-case relationship category will be summarized.

Serious Adverse Events (SAEs) will also be summarized by relationship.

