2.2 Secondary objective

To evaluate the safety and tolerability of CPC-201 as a function of dose and initial rate of dose titration.

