20170802_Chase_CPC-001-12_SAP_Final Version 1.0.docx Confidential

during a two week run in period; donepezil treatment will continue at 10mg/day. Once on 15 mg/day of solifenacin for two weeks (based upon the investigator judgment), the donepezil dose will be increased at weekly or bi-weekly intervals, in accordance with the schedules given below, to its first intolerable dose (FID) or maximum allowed dose (MAD) of 60mg/day

Cohort 1b	1st-2nd week: 10mg donepezil + 15mg solifenacin 3rd week: 20mg donepezil + 15mg solifenacin 4th week: 30mg donepezil + 15mg solifenacin 5th week: 40mg donepezil + 15mg solifenacin 6th week: 50mg donepezil + 15mg (or 20mg) solifenacin 7th week: 60mg donepezil + 15mg (or 20mg) solifenacin
-----------	--

Second Amendment

[figure not shown]
After 6 subjects were enrolled in Cohort 1b, the protocol was amended to add Cohort 3c.

All subjects entering the study in cohort 3 will start with a dose regimen of 10mg donepezil + 15mg solifenacin and will continue to increase the donepezil dose by 5mg increments every 7 days (or up to 14 days per PI discretion) up to 40mg or the MTD.

Cohort 3c	1st week: 10mg donepezil + 15mg solifenacin 2nd week: 15mg donepezil + 15mg solifenacin 3rd week: 20mg donepezil + 15mg solifenacin 4th week: 25mg donepezil + 15mg solifenacin 5th week: 30mg donepezil + 15mg solifenacin 6th week: 35mg donepezil + 15mg solifenacin 7th week: 40mg donepezil + 15mg solifenacin
-----------	---

All the schedule of assessments for this study are presented in the protocol and also in the Appendix 1 of this SAP.

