3. SAMPLE SIZE DETERMINATION

No formal sample size calculation has been made. Based on experience from previous similar studies, a total 4-6 evaluable subject per group per cohort is considered sufficient.

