5. HYPOTHESIS TO BE TESTED

There is no formal hypothesis testing for this study. The study is not powered to reliably yield statistically significant conclusions.

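### The by-cohort TEAE percentages in SAP 8.3.1.1 mix titration schedule with observation time and dose, so they cannot be read as a comparison of titration rates

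*SAP*

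**What the plan says.** The protocol's secondary objective (section 2.2) is to evaluate safety and tolerability "as a function of dose and initial rate of dose titration". SAP 8.3.1 repeats the intention to analyse safety by dose and by titration schedule, but gives no method or denominator.

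The TEAE summaries listed in SAP 8.3.1.1 include one "By cohort (*i.e.*, 1, 2, 1b, 3c" and, as a separate item, one "By study phase (*i.e.*, titration and long term extension". A TEAE is any event starting at or after the first dose; no closing date is given. Each subject counts once at each level of summary, and SAP 8 reports categorical data as counts and percentages. The visible text has no patient-weeks, exposure-adjusted rate, time-to-event summary or common window for adverse events, and no by-dose TEAE table is listed.

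Protocol 9.1.2 plans AE tables by study period and treatment group. The study is descriptive: "There is no formal hypothesis testing for this study", and "No formal sample size calculation has been made".

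**The concern.** The schedules being compared differ in length by design, so a subject on a longer schedule has more time in which to have an event. They also differ in dose: Cohorts 1, 2 and 1b go to 60 mg and Cohort 3c stops at 40 mg. A percentage that counts each subject once absorbs both differences. If extension events are included, it also absorbs optional extra time that varies between subjects.

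The by-cohort table is the only AE summary by schedule in the SAP's list, and the aim of the study is to choose a titration schedule. A reader who takes a difference between cohort percentages as an effect of titration rate could be looking at an effect of follow-up or dose instead.

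**Working it through.** **1. Scheduled titration time (SAP 2.1).** The last steps are "5 th week: 60mg donepezil + 15mg (or 20mg) solifenacin" for Cohort 1, "3 rd week: 60mg donepezil + 15mg (or 20mg) solifenacin" for Cohort 2 and "7th week: 60mg donepezil + 15mg (or 20mg) solifenacin" for Cohort 1b. Cohort 3c has seven one-week steps from 10 to 40 mg.

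- Cohort 2: 3 weeks. Cohort 1: 5 weeks.
- Cohort 1b: 2 + 5 × 1 = 7 weeks. Cohort 3c: 7 × 1 = 7 weeks.

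The 7 weeks for 1b and 3c reproduce the maximum dosing duration in the Protocol Summary. The planned spread is 7/3 = 2.3-fold. With the longer intervals that the plan permits, 1b takes 2 + 4 × 2 + 1 = 11 or 2 + 5 × 2 = 12 weeks, and 3c takes 6 × 2 + 1 = 13 or 7 × 2 = 14 weeks. These exceed the stated 7 weeks, so the passages must be reconciled.

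**2. Effect of time alone.** The weekly hazards *h* here are assumptions. For *w* weeks, P(at least one TEAE) = 1 − exp(−*h* × *w*).

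| *h* per week | 3 weeks | 5 weeks | 7 weeks | Gap, 3 to 7 weeks |
|---|---|---|---|---|
| 0.05 | 14% | 22% | 30% | 16 points |
| 0.10 | 26% | 39% | 50% | 24 points |
| 0.20 | 45% | 63% | 75% | 30 points |

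**3. Effect of time and dose together.** Now let the hazard rise with dose, with an assumed 0.10 per week at 20 mg.

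- Proportional to dose: P = 1 − exp(−0.10 × mg-weeks / 20).
- Proportional to dose squared: P = 1 − exp(−0.10 × Σ(mg² × weeks) / 400). The sums are 5,600 (Cohort 2), 9,000 (Cohort 1), 9,200 (1b) and 5,075 (3c).

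| Cohort | Weeks | mg-weeks | Mean mg/day | Constant, 0.05 | Proportional to dose | Dose squared |
|---|---|---|---|---|---|---|
| 2 | 3 | 120 | 40 | 14% | 45% | 75% |
| 1 | 5 | 200 | 40 | 22% | 63% | 89% |
| 1b | 7 | 220 | 31.4 | 30% | 67% | 90% |
| 3c | 7 | 175 | 25 | 30% | 58% | 72% |

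Within each of the last three columns the weekly risk at a given dose is the same in every cohort, so titration rate as such has no effect. The percentages still differ, and the ordering changes: 3c ties for highest under a constant hazard, falls below the shorter Cohort 1 when risk is proportional to dose, and is lowest of all under dose squared. Steps 2 and 3 assume the full schedule is completed at weekly steps; early stopping at the first intolerable dose and extension time are left out.

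**4. What a rate does.** Under a constant hazard, expected first events per subject are 1 − exp(−*hw*) and expected time at risk is [1 − exp(−*hw*)]/*h*, so their ratio is *h* whatever the schedule length. At *h* = 0.10 the rate is 0.10 per patient-week in every cohort, while the crude percentages run 26%, 39% and 50%. The rate removes the time effect but not the dose effect, hence the need for a by-dose summary too.

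**5. Precision.** Exact (Clopper-Pearson) 95% intervals are 12–88% for 3/6 and 16–84% for 4/8. With one subject the percentage can only be 0 or 100.

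**The case against.** Four points can be made for the plan as it stands.

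- **Direction.** A reader might infer that slower titration will look less safe simply because it is observed longer. The documents do not support that. It follows only if weekly risk does not depend on dose, whereas the trial escalates to a first intolerable dose, and 3c is slow but has the lower ceiling (175 scheduled mg-weeks against 200 in Cohort 1). This objection stands: the distortion has no fixed sign.
- **Size.** A reader might take the contrast to be 3 against 14 weeks. Fourteen weeks requires every 3c step, including the last, to use the discretionary 14 days; the planned spread is 3 to 7. The short end may also rest on very few subjects: SAP 2.1 reports one subject in Cohort 2 at the first amendment and gives no final number. A 16-point shift is well inside the noise of a study that tests nothing. This limits how much any version of the table can show, but it does not justify omitting the denominator.
- **Extension.** A reader might infer that the cohort table certainly includes extension events. That is not established. The SAP also summarises by phase, the protocol plans tables by study period, and no table shells are visible. What stands is that the SAP does not say cohort and phase are crossed. The extension's length is not visible, so its contribution cannot be sized.
- **Recoverability.** AE onset and stop dates, dosing data and time to first intolerable dose are to be listed, so a reader could reconstruct exposure by hand. That is true at this sample size, but it also shows that the sponsor can tabulate it at little cost.

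**Conclusion.** The point holds in a limited form. Followed as written, SAP 8.3.1.1 gives crude cohort percentages over unequal observation time and unequal dose, possibly with extension events added, and these cannot be read as a comparison of titration rates. Over the planned 3 to 7 weeks, time alone could move the percentage by 16 to 30 points at assumed constant hazards of 0.05 to 0.20 per week. With dose-dependent risk the effect can shrink or reverse. The structural part rests on the schedules and counting rule in the documents; the size rests on assumed hazards. Because the analysis is descriptive and the cohorts are small, this is a cheap improvement to the reporting and does not invalidate the study.

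**What to change.** - Produce the by-cohort TEAE table for the titration phase only, and state when the titration TEAE window ends. This is in line with the by-period tables in protocol 9.1.2.
- Beside n (%), show total patient-weeks at risk and subjects with a first event per patient-week.
- Give the same columns by donepezil dose level, which supplies the by-dose analysis that SAP 8.3.1 already promises.
- Report the extension separately, with its own patient-weeks.
- Reconcile the 7-week dosing duration with the permitted bi-weekly and 14-day steps.

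The proportion with an event by completion of 40 mg should not be used as a common yardstick. Cohorts 2, 1, 1b and 3c complete 40 mg after 2, 3, 5 and 7 weeks, a 3.5-fold spread that is wider than the 2.3-fold spread in planned titration. At a constant 5% per week it would give 10%, 14%, 22% and 30% with no true difference.

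The cost is a few extra columns and a by-dose table, built from dosing records and AE onset dates that are already collected. The downside is that person-time rates assume a roughly constant hazard and are very imprecise at about 6 subjects per group, so they should stand beside the crude counts and be read descriptively.
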